8.10 Development safety update reports

The Chief Investigator will provide Development Safety Update Reports (DSURs) once a year throughout the clinical trial, or as necessary, where relevant to the REC and the Sponsor.

The report will be submitted within 60 days of the Developmental International Birth Date (DIBD) of the trial each year until the trial is declared ended.

9 STATISTICAL ANALYSIS PLAN

9.1 Sample size calculation

Based on an effect size of $d = 0.70$ (Meron et al., 2015; Mutz et al., 2018) following a 6-week course of tDCS treatment (consisting of 15-21 sessions) with 90% power, we will enrol 50 participants to achieve a sample size of 45 participants with bipolar depression who will complete the course of treatment, based on a 10% attrition rate.

[figure not shown]

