Trial Name:

Community-based transcranial direct current stimulation treatment for bipolar depression

Document date:

17/07/2023

Principal Investigator	[name][name], University of East London, [name]
Protocol contributors	[name], Centre for Affective Disorders, Institute of Psychiatry, Psychology and Neuroscience, King's College London [name], Technische Universität Dresden, Germany [name], Technische Universität Dresden, Germany [name], University College London
Clinicaltrials.gov ID	NCT05436613
Funders	Milken Institute (financial support) Flow Neuroscience (provision of Flow tDCS device)

Contents

TRIAL SUMMARY	2
1 RATIONALE	5
2 OBJECTIVES AND OUTCOME MEASURES/ENDPOINTS	5
3 TRIAL DESIGN	7
4 TRIAL SETTING	7
5 PARTICIPANT ELIGIBILITY CRITERIA	7
6 TRIAL PROCEDURES	8
7 TRIAL TREATMENTS	10
8 RECORDING AND REPORTING OF ADVERSE EVENTS	11
9 STATISTICAL ANALYSIS PLAN	14
10 REFERENCES	17
11 SCHEDULE OF EVENTS	18

TRIAL SUMMARY

Trial Title:	Community-based transcranial direct current stimulation treatment for bipolar depression	
Short Title:	Transcranial direct current stimulation therapy for bipolar depression (b-DEP)	
Trial Design:	Pilot, open-label, single arm design	
Trial Participants:	Participants will have a diagnosis of Bipolar disorder, in a current depressive episode of moderate severity, receiving pharmacological or psychological treatment, ages minimum 18 years, community-dwelling.	
Total number of participants planned:	50	
Treatment duration:	6 weeks	
Additional follow up duration:	3 months	
Total trial duration per participant:	5 months	
Estimated total trial duration:	1 year	
Planned trial sites:	Multi-site	
	Objectives	Outcome Measures
Primary Objective:	To assess the efficacy of tDCS treatment	clinical response as measured by MADRS score improvement of $\geq 50\%$ following the course of tDCS treatment
Secondary Objective:	To assess acceptability and safety of the intervention.	Participant retention at the end of the treatment who have completed a minimum of 15 tDCS sessions. Participant acceptability questionnaire scales tDCS Adverse Events Questionnaire at each session

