2.6 Exploratory endpoints/outcomes

Exploratory measures:

- i. Trained rater measure of depressive symptoms: Montgomery–Åsberg Depression Rating Scale (MADRS) remission rate
- ii. Self-report measure of depressive symptoms: Patient Health Questionnaire (PHQ-9)
- iii. Trained rater measure of anxiety symptoms: Hamilton Anxiety Scale (HAMA)
- iv. Trained rater measure of manic symptoms: Young Mania Rating Scale (YMRS)
- v. Self-report measure of disability and impairment: Sheehan Disability Scale (SDS)
- vi. Self-report Quality of Life Enjoyment and Satisfaction Questionnaire (Q-LES-Q)
- vii. Self-report acceptability of tDCS from healthy controls.
- viii. EEG recordings will be acquired during an eyes-closed resting state for 10 minutes and eyes open resting state for 10 minutes using a mobile EEG device in participants' homes (Muse EEG; <https://choosemuse.com/>) (Hashemi et al., 2016). Resting state EEG will be acquired at baseline for healthy controls and at 2 timepoints for participants with bipolar depression: 1) at baseline, and 2) at the end of the 6-week course of treatment. EEG coherence, a measure of neural connectivity, will be examined as a potential surrogate outcome measure (Minuissi et al., 2012).
- ix. Neuropsychological measures: verbal learning (Rey Auditory Verbal Learning Test (RAVLT)) and information processing speed (Symbol-Digit Modalities Test (SDMT)) will be assessed in participants' homes. Neuropsychological assessments will be delivered to participants and administered by a research team member via video call. Our pilot data indicates feasibility and acceptance of the neuropsychological assessments as all participants had completed the assessments (26 out of 26 participants). The measures will be acquired at baseline for healthy controls, and at 2 timepoints for participants with bipolar depression: 1) at baseline, and 2) at the end of the 6-week course of treatment.

Exploratory outcomes:

- 1) MADRS score ≤ 9 following the course of tDCS
- 2) Improvement in self-reported depressive symptoms as measured by PHQ-9
- 3) Improvement in anxiety symptoms as measured by HAMA
- 4) No significant increase in manic symptoms as measured by YMRS score >13
- 5) Improvement in disability experience as measured by SDS
- 6) Improvement in quality of life as measured by Q-LES-Q
- 7) Healthy control participant baseline acceptability questionnaire.

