6.1 Recruitment

Based on an effect size of $d = 0.70$ (Meron et al., 2015; Mutz et al., 2018) following a 6-week course of tDCS treatment (consisting of 15-21 sessions) with 90% power, we will enrol 50 participants to achieve a sample size of 45 participants with bipolar depression who will complete the course of treatment, based on a 10% attrition rate.

We will enrol 35 healthy controls to complete baseline activities.

Our participants have a wide ethnic diversity. In our pilot study, 38% of participants were of non-White ethnicity i.e. 12% Black/African Caribbean, 4% Pakistani, 4% Chinese, 16% Mixed ethnic background, and 62% English or any White background. Recruitment will be from primary care, consulting psychiatrists, print and social media advertisements.

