6.3 The randomisation scheme: N/A

6.3.1 Method of implementing the randomisation/allocation sequence: N/A

6.4 Blinding: N/A

6.5 Emergency Unblinding: N/A

6.6 Baseline data

The baseline data consist of: MADRS, tDCS AEQ, Acceptability questionnaire, PHQ-9, HAMA, YMRS, SDS, Q-LES-Q, EEG, AVLT, SDMT (Appendix 2).

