9.3.2 Primary outcome analysis

The primary outcome analysis clinical response which will be measured by the number of enrolled participants who show a clinical response at the end of treatment (MADRS score improvement of $\geq 50\%$ following the course of tDCS treatment), divided by the total number of enrolled participants, expressed as a percentage.

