9.4 Subgroup analyses: N/A

9.5 Adjusted analysis: N/A

9.6 Interim analysis and criteria for the premature termination of the trial: N/A

9.7 Participant population

All participants will be included in the analysis in an intention to treat analysis and participants who have completed the study will be included in a completer analysis.

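### The 90% power claimed for d = 0.70 does not belong to the planned primary analysis, a single-arm response percentage with no test or reference rate, and no precision is stated

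*Combined protocol and SAP*

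**What the plan says.** Sections 6.1 and 9.1 give the same justification: an effect size of d = 0.70 taken from two meta-analyses, and "with 90% power, we will enrol 50 participants to achieve a sample size of 45 participants with bipolar depression", with 10% attrition linking the two numbers. The text names no endpoint, comparison, test or alpha for this calculation. A figure after 9.1 is not shown in the available copy.

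The Trial Summary describes a "Pilot, open-label, single arm design", and the protocol states "6.3 The randomisation scheme: N/A". The only other group takes no part in treatment: "We will enrol 35 healthy controls to complete baseline activities" (section 6.1).

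The primary endpoint (2.4) is binary: MADRS improvement of at least 50%. Section 9.3.2 analyses it as the number of responders "divided by the total number of enrolled participants, expressed as a percentage". Section 9.7 adds that "participants who have completed the study will be included in a completer analysis". Sections 9.3 to 9.9 contain no hypothesis test, reference rate, success threshold or confidence interval. Section 9.9, on other statistical considerations, is marked not applicable.

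**The concern.** Three features of the calculation fail to match the analysis.

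- **Scale.** The effect size d is a standardised difference in means. The primary endpoint is a proportion.
- **Comparison.** Power requires a test against something. Section 9.3.2 compares the response rate with nothing.
- **Denominator.** The calculation targets 45 completers, while 9.3.2 divides by everyone enrolled. This is the least of the three, because 9.7 also plans a completer analysis.

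The primary objective is efficacy (2.1), so a reader will take the trial to be 90% powered to show efficacy. The findings are also meant to feed the design of a randomised sham-controlled trial (section 1). Whoever plans that trial needs to know how uncertain the response rate is, and the plan neither states the expected uncertainty nor commits to reporting an interval.

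**Working it through.** **Inputs.** From 6.1 and 9.1: d = 0.70, power 90%, 45 completers, 50 enrolled, attrition 10%. From 6.1: 35 healthy controls. Alpha is not in the available text; two-sided 5% is assumed below unless stated.

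**1. The attrition step.** 45 / (1 − 0.10) = 50. This reproduces exactly.

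**2. Where 45 could come from.**

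- *Two-group comparison of means.* Normal approximation: n per group = 2(1.960 + 1.282)² / 0.70² = 42.9, so 43. By t-test, 43.9, so 44. Power at 45 per group is 90.7%.
- *One-sample or paired t-test, d scaled to the SD of change.* Normal approximation: n = (1.960 + 1.282)² / 0.70² = 21.4, so 22. By t-test, 23.4, so 24. Power at 45 is 99.6%.
- *Paired t-test, d scaled to the raw-score SD.* Here dz = 0.70 / √(2(1 − r)), where r is the correlation between the scores before and after treatment. At r = 0, dz = 0.495 and n = 44.9, so 45 (power 90.1%). At r = 0.1, 0.3 and 0.5, n is 40.6, 32.0 and 23.4.
- *45 patients against 35 healthy controls at baseline.* Power is 86.6%, so this does not give 90%.

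Thus 45 fits one arm of a two-group comparison that this trial does not make, or a paired test with zero pre-post correlation. Its origin is not established. Both routes concern means; neither concerns a response rate.

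**3. Is there another planned analysis for the power to attach to?** Mean MADRS change is not an endpoint in 2.3 to 2.7; the exploratory MADRS measure is the "Depression Rating Scale (MADRS) remission rate". Section 2.6 does list improvement in PHQ-9, HAMA, SDS and Q-LES-Q, but section 9.3 gives no test for any of them. The plan therefore assigns the power to no analysis.

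**4. What the sample does provide.** Exact (Clopper-Pearson) 95% intervals for x responders among n have limits Beta(0.025; x, n − x + 1) and Beta(0.975; x + 1, n − x). Half-width means half the distance between the limits.

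| n | Responders | 95% CI | Half-width (points) |
|---|---|---|---|
| 50 | 25 (50%) | 35.5% to 64.5% | 14.5 (maximum) |
| 50 | 10 (20%) or 40 (80%) | 10.0% to 33.7%, or 66.3% to 90.0% | 11.8 |
| 45 | 22 (49%) | 33.7% to 64.2% | 15.3 (maximum) |
| 45 | 9 (20%) or 36 (80%) | 9.6% to 34.6%, or 65.4% to 90.4% | 12.5 |

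**5. What power would look like if a reference rate were named.** The documents give none, so reference rates p0 from 5% to 50% and a true rate of p0 + 20 points are assumptions. With n = 50, take the smallest r for which P(X ≥ r | p0) ≤ alpha; power is then P(X ≥ r | p0 + 0.20).

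- One-sided 0.025: lowest 76.0% (30% against 50%, r = 23), highest 98.1% (5% against 25%).
- One-sided 0.05: lowest 83.9%, highest 99.3%.

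No single power figure holds without a named rate and alpha.

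**The case against.** This is a pilot, proof-of-concept study, and a descriptive percentage is an acceptable primary analysis for one. Nothing above shows that 50 is too few. The figure missing after 9.1 may contain the test and alpha, so their absence from the text cannot be held against the plan. The completer analysis in 9.7 explains why 45 completers are of interest. Continuous exploratory scales exist to which a standardised effect could attach. Any account of how 45 was reached is conjecture, and a Wilson interval would serve as well as an exact one.

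Most of this is right and limits the finding. The sample size is not challenged, the missing alpha is not counted as a fault, and the origin of 45 is left open. The mismatch remains. A figure in 9.1 could define a test for d, but it would not put a comparison into 9.3.2. The completer analysis of the primary endpoint is again a percentage. The exploratory scales have no named test, and powering one of them would not power the response rate. That the study is a pilot is itself a reason to justify its size by precision. The choice between interval methods is immaterial; the defect is that no interval is planned.

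**Conclusion.** The concern holds. The plan claims 90% power in two places, but its primary analysis contains no test for that power to describe, and it states no precision for the quantity it will report. The attrition arithmetic is correct and the response percentage remains computable, so this is a fault in the stated justification and not a threat to the trial's feasibility. It should be fixed.

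The size of the omission is the unstated uncertainty: up to 14.5 points either side with 50 enrolled, or 15.3 with 45 completers. These half-widths depend only on n and the 95% level. The t-test figures assume two-sided 5%, and the binomial power range assumes reference rates and a 20-point gain that the documents do not supply; the conclusion depends on neither.

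**What to change.** In 6.1 and 9.1, remove the 90% power statement as the justification for the primary analysis. State instead that 50 enrolled participants give a two-sided exact 95% confidence interval for the response proportion with a half-width of at most about 14.5 percentage points, or about 15.3 with 45 completers. In 9.3.2, commit to reporting the Clopper-Pearson 95% interval with the percentage.

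If the sponsor wishes to keep a power figure, there are two ways:

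- attach it to a named test, for example on mean MADRS change added as an endpoint, and give the alpha and the SD by which d is scaled; or
- name and justify a reference response rate, and give exact binomial power at n = 50 with its alpha.

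The cost is wording in the protocol and SAP plus one interval in the primary analysis. Enrolment, visits and measurements stay as they are; the schedule of events already includes MADRS before treatment and at its end. The drawback for the sponsor is that a favourable power claim gives way to an interval of roughly 14.5 points either side.

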9.2 Planned recruitment rate

The planned recruitment rate is 4-6 participant/s per month.

9.3 Statistical analysis plan

9.3.1 Summary of baseline data and flow of patients

Consort Flow Diagram:

9.3.2 Primary outcome analysis

The primary outcome analysis clinical response which will be measured by the number of enrolled participants who show a clinical response at the end of treatment (MADRS score improvement of $\geq 50\%$ following the course of tDCS treatment), divided by the total number of enrolled participants, expressed as a percentage.

9.3.3 Secondary outcome analysis

The secondary outcome analyses are; participant retention, which will be measured by the number of enrolled participants who do not drop out before the 6 week course of tDCS, divided by the total number of enrolled participants, expressed as a percentage; Acceptability, which will be measured by the percentage of participants rating the intervention as acceptable at the end of the 6 week course of tDCS. The acceptability scale consists of the question 'How acceptable did you find the tDCS

sessions?' with responses ranging from 'Very unacceptable' to 'Very acceptable' on a 7-point anchored Likert scale with the acceptable ratings being from rating 5-7, and safety outcomes, which will be measured by calculating the number of severe, moderate and mild adverse events and their relation to the intervention.

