1.1 Assessment and management of risk

Noninvasive transcranial direct current stimulation (tDCS) has been used in human for decades. These noninvasive current stimulation techniques use battery-powered current generator devices that have a built-in circuitry to limit the current above a certain level, typically 2 mA.

The most common **adverse events** are mild skin redness (54%) at the site of the electrodes, which resolves following stimulation, itching (39%) and tingling (22%), followed by headache (16%), discomfort (13%) and burning sensation (10%) (Brunoni et al., 2011, Sampaio-Junior et al., 2018). There is no significant difference in rates between active and sham tDCS, except for skin redness which is more common with active (54%) relative to sham tDCS (19%) (Sampaio-Junior et al., 2018). Participants have been unable to distinguish whether they were receiving active or sham tDCS though, and there have been no differences in the discontinuation rates for active and sham treatments, mean rates 10% and 12%, respectively (Meron et al., 2015). In our recent pilot study in unipolar depression, the discontinuation rate has been 7.6% (2 out of 26 enrolled participants).

The **risk of treatment-emergent mania or hypomania** is estimated to be around 4% with a course of active tDCS and 0.5% with sham tDCS, with no statistical difference between active and sham tDCS (Brunoni et al., 2017; Sampaio-Junior et al., 2018). While the rate is lower than the 5-9% risk associated with antidepressant medication, it might be higher than the risk of <1% associated with repetitive transcranial magnetic stimulation (Xia et al., 2008).

Protocols in human trials (≤ 40 min, ≤ 4 milliamperes, ≤ 7.2 Coulombs) have not produced any reports of serious adverse effect or irreversible injury with over 33,200 sessions and 1,000 participants with repeated sessions (Bikson et al., 2016).

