2.7 Table of endpoints/outcomes

Objectives	Outcome Measures	Timepoint of evaluation of this outcome measure
Primary Objective To assess the efficacy of tDCS treatment.	Clinical response as measured by MADRS score improvement of >= 50% following the course of tDCS treatment	End of tDCS sessions (visit 21)
Secondary Objectives To assess the acceptability and safety of the intervention	Participant retention at the end of the treatment who have completed a minimum of 15 tDCS sessions Participant acceptability questionnaire scales tDCS Adverse Events Questionnaire	End of tDCS sessions (visit 21) At each session

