6.10 Withdrawal criteria

Participants will be withdrawn from the trial if they do not comply with the intervention, namely if they are unable to have a minimum of 50% of the tDCS session (10 out of 21 sessions), or if they develop serious adverse effects from any part of the study. Recording of the reasons for withdrawal will be made. Should a participant lose capacity to consent during the study then they would be withdrawn from the study, and that their identifiable data already collected with consent would be retained for use, and that no further data collection would take place. Their GP will be informed about their withdrawal, and there will have a telephone follow up at 1 month following their withdrawal.

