7.4 Drug storage and supply (if applicable): N/A

7.5 Preparation and labelling of Investigational Medicinal Product (if applicable): N/A

7.6 Dosage schedules:

The Flow Neuroscience tDCS headset will be delivered to the participant's home. The device is designed and approved (CE) to be used at home without supervision.

6-week course of active tDCS treatment, consisting of 5 sessions per week for the first 3 weeks followed by 2 sessions per week for 3 weeks, for a total of 21 tDCS sessions. Duration of each session is 30 minutes. We will use the Flow Neuroscience tDCS device (Figure 1) with a bifrontal montage: anode at left dorsolateral prefrontal cortex (DLPFC) and cathode at right DLPFC (EEG positions F3 and F4, respectively). Stimulation is 2 mA, and electrode area is 35 cm². During each session, participant will be seated comfortably with their eyes open, and research assistant will provide a discreet presence without interacting with the participant by video call.

tDCS parameters are based on meta-analyses (Meron et al., 2015; Dondé et al., 2017; Mutz et al., 2018) indicating that effects are greatest at 2 mA current of 30-minute stimulus. The tDCS equipment records the duration of each session, and there is an automatic shut-off to prevent unsafe use.

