7.11 Assessment of compliance with treatment

The tDCS device records the duration of each session, and there is an automatic shut-off to prevent unsafe use. The equipment will be programmed to provide only the type of stimulation, intensity and session length that are specified in the protocol. The placement is determined by the location of the electrodes which are fitted to the headset. The research assistant will be present at each session, in person or via video link, in order to aid in the initial positioning and to monitor for any adverse events.

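### The retention formula in SAP 9.3.3 leaves out the 15-session minimum that defines the retention endpoint in the trial summary, 2.5 and 2.7

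*Combined protocol and SAP*

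**What the plan says.** The trial summary, section 2.5 and the table in 2.7 state the endpoint in the same words: "Participant retention at the end of the treatment who have completed a minimum of 15 tDCS sessions". The table sets its timepoint at "End of tDCS sessions (visit 21").

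Section 9.3.3 is the only place that says how retention is calculated. Its numerator is the "number of enrolled participants who do not drop out before the 6 week course of tDCS", its denominator is the total enrolled, and the result is a percentage. It mentions no session count, and section 9 nowhere defines dropout.

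Three other places bear on the point:

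- Section 7.6 sets the course at "5 sessions per week for the first 3 weeks followed by 2 sessions per week for 3 weeks".
- Section 6.10 withdraws participants who are "unable to have a minimum of 50% of the tDCS session (10 out of 21 sessions").
- Section 9.1 plans for "a sample size of 45 participants with bipolar depression who will complete the course of treatment, based on a 10% attrition rate".

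**The concern.** A condition stated three times as part of the endpoint is missing from the sentence that computes it. An analyst working from 2.5 and another working from 9.3.3 can report different retention percentages from the same data, and the choice between the two rules could be made after the data are seen.

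The 9.3.3 wording also has two possible readings. Literally, a person fails only by dropping out before the course, so someone who leaves after the first session is retained. If the words 'the end of' were meant, a person who stays to week 6 is retained however few sessions they had. The 15-session condition is absent either way.

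Retention is the first listed secondary endpoint and speaks to acceptability, a stated secondary objective. Section 1 says the findings will be applied to the design of a randomised sham-controlled trial.

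**Working it through.** **Schedule.** From 7.6, 5 × 3 + 2 × 3 = 21 sessions. The schedule of events puts treatment on days 1–5, 8–12 and 15–19 (15 sessions), then days 22, 25, 29, 32, 36 and 39 (6 sessions). Session 15 therefore falls on day 19 and session 21 on day 39. A participant on schedule who leaves between those days has 15 to 20 sessions.

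**Thresholds.** The endpoint minimum is 15/21 = 71.4% of sessions. The withdrawal rule in 6.10 gives 50%, which is 10.5 sessions, and also 10 of 21, which is 47.6%. A participant with 11 to 14 sessions clears 6.10 on either figure and still fails the endpoint.

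**Who counts as retained.** The endpoint wording can mean both conditions (the natural reading, given the end-of-treatment timing and visit 21) or a session count alone.

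| Group | 2.5: both conditions | 2.5: count alone | 9.3.3: literal | 9.3.3: end of course |
|---|---|---|---|---|
| A: stays to week 6, ≥15 sessions | yes | yes | yes | yes |
| B: stays to week 6, <15 sessions | no | no | yes | yes |
| C: leaves early, ≥15 sessions | no | yes | yes | no |
| D: leaves early, <15 sessions | no | no | yes | no |
| E: never starts | no | no | no | no |

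The gap, as 9.3.3 minus 2.5:

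- literal minus both conditions = B + C + D
- end of course minus both conditions = B
- literal minus count alone = B + D
- end of course minus count alone = B − C, which can have either sign

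**Size per participant.** 1/50 = 2 percentage points.

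**Planned attrition (9.1).** The plan's own figure reproduces: 50 × (1 − 0.10) = 45. Assume all 45 completers reach 15 sessions, so A = 45, B = 0 and C + D + E = 5.

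- Both conditions: 45/50 = 90%.
- Literal 9.3.3: (50 − E)/50, which is 90% if all 5 leavers never start (E = 5) and 100% if all 5 leave after starting (E = 0). The gap is 0 to 10 points.
- End-of-course 9.3.3: 45/50 = 90%. The gap is 0.

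**Pilot attrition (1.1).** There "the discontinuation rate has been 7.6% (2 out of 26 enrolled participants"). That pilot was in unipolar depression, so carrying it over is an assumption. 50 × 2/26 = 3.8, or about 4 leavers. Under the same assumption about completers, the endpoint rate is 46/50 = 92% and literal 9.3.3 gives 92% to 100%, a gap of 0 to 8 points.

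**End-of-course reading with some low attenders.** If k of 45 stayers have fewer than 15 sessions, 9.3.3 still gives 90% while the endpoint with both conditions is (45 − k)/50: 88% for k = 1, 86% for k = 2, 84% for k = 3, 80% for k = 5. These values of k are illustrations; the documents give no expected number.

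**The case against.** The strongest reply is that the larger gaps come from a slip of wording. The measure is called retention, the next outcome in the same paragraph is timed at the end of the 6-week course, and the endpoint itself is placed at the end of treatment, so dropout before the end of the course is probably what was meant. On that reading the plan's own figures show no gap. To create one, a participant would have to miss at least 7 of 21 sessions, stay to about day 39 and not be withdrawn under 6.10. Nothing in the documents suggests this would be common. All of that stands, and the 0 to 10 and 0 to 8 point ranges apply only to the literal reading.

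A second reply is that 9.1 describes the 6-week course as 15 to 21 sessions, so not dropping out of the course could imply reaching 15. This does not carry. The phrase sits in the effect-size justification, the trial summary and 7.6 fix the course at 21 sessions, and 9.3.3 counts people who drop out, not sessions attended. Nothing links the two.

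A third reply is that retention is descriptive, has a clear definition in three places, and can be reported both ways later because sessions are recorded. That limits the seriousness. It does not remove the conflict between the endpoint and its formula.

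**Conclusion.** The concern holds. As written, 9.3.3 need not produce the retention endpoint stated in the summary, 2.5 and 2.7, and no definition elsewhere in the plan restores the 15-session condition.

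If the endpoint requires both conditions, 9.3.3 equals or overstates it. If it means a session count alone, literal 9.3.3 again equals or overstates it, but the end-of-course reading can err in either direction.

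The plan's figures bound the gap at 10 points on the literal reading, assuming every planned completer reaches 15 sessions. On the more plausible end-of-course reading, with both conditions required, the gap is 2 points for each participant who stays with fewer than 15 sessions, and may be zero. The consequence is modest: no threshold, test or decision depends on retention. It should still be corrected before analysis, because it is a reported secondary result.

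**What to change.** In 9.3.3, define the numerator as enrolled participants with bipolar depression who have not dropped out by the end of the 6-week course and have completed at least 15 tDCS sessions, over all enrolled participants with bipolar depression. This carries over the minimum already in 2.5 and 2.7. Naming the population also makes clear that the 35 healthy controls in 6.1, who are enrolled for baseline activities only, are not in the denominator. If a session count alone was intended, both 2.5 and 9.3.3 should say so before analysis.

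Separately, the two figures in the 6.10 withdrawal rule do not agree with each other and must be reconciled; this review does not choose between them.

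The cost is one sentence. No new data are needed: 7.11 notes that "The tDCS device records the duration of each session" and that a research assistant is present at every session, so completed sessions can be counted. The reported retention rate may be slightly lower.

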2.5 Secondary endpoints/outcomes

- 1) Participant retention at the end of the treatment who have completed a minimum of 15 tDCS sessions
- 2) Participant acceptability questionnaire scales
- 3) tDCS Adverse Events Questionnaire at each session (Brunoni et al., 2011)

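### Section 9.3.3 reports safety only as a number of adverse events, with no participant denominator and no rule for repeats, so the share of participants harmed cannot be recovered from it

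*Combined protocol and SAP*

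**What the plan says.** Safety is a secondary objective (section 2.2). Its endpoint in section 2.5 is the "tDCS Adverse Events Questionnaire at each session". Section 9.3.3 then gives the analysis as "calculating the number of severe, moderate and mild adverse events and their relation to the intervention". That is the whole specification. It does not state a denominator, a count of participants with at least one event, a rate per session, or whether a recurrence at the next session is a new event.

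The other two outcomes in the same section are proportions of people. Retention is "divided by the total number of enrolled participants, expressed as a percentage", and acceptability is "the percentage of participants rating the intervention as acceptable". The primary outcome in section 9.3.2 is also a percentage of enrolled participants.

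Four other parts of the plan bear on how the count would behave:

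- Section 7.6 sets the course at three weeks of five sessions and three weeks of two, "for a total of 21 tDCS sessions". Section 9.1 describes a course "consisting of 15-21 sessions", and section 6.10 ties withdrawal to a "minimum of 50% of the tDCS session (10 out of 21 sessions". Exposure will therefore differ between participants.
- Section 8.9 extends recording of adverse events to 3 months after the last session.
- Section 9.8 fills in all missing data by last observation carried forward (LOCF).
- Section 9.7 names an intention-to-treat and a completer analysis, but does not say which applies to safety and does not turn the event count into a proportion.

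**The concern.** When the same question is put to the same person at up to 21 sessions, a total of events depends on three things: how many people were affected, how often the event came back in each of them, and how many sessions each of them had. Section 1.1 describes the commonest effect, skin redness, as clearing after stimulation, so it can begin afresh at every session. A few people with redness every time and many people with redness once can give the same total.

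This matters for two reasons. Section 1.1 gives its background figures as percentages (redness 54%, itching 39%, tingling 22%, treatment-emergent mania or hypomania about 4%), and a bare event count cannot be set against a percentage. Section 1 says the findings will inform the design of a sham-controlled trial, for which the natural safety input is the proportion of participants with an event. If the plan does not fix that summary, the counting rule and the denominator will be chosen after the data have been seen.

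**Working it through.** The documents state no figure for the safety outcome, so there is none to reproduce. The figure that would supply its denominator can be reproduced: section 9.1 has 45 completers and 10% attrition, and 45 / (1 − 0.10) = 50 enrolled.

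**Inputs**

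- Participants: 50 (sections 6.1 and 9.1).
- Sessions: 5 × 3 + 2 × 3 = 21 (section 7.6).
- Occasions on which an event can be elicited during treatment: at most 50 × 21 = 1,050.
- Redness: 54% (section 1.1). The section does not state the unit. I assume participants, giving 0.54 × 50 = 27.
- Assumption throughout: at most one such event per person per session.

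**Recurrence, with the affected share held at 27 of 50**

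Events = affected participants × sessions × share of sessions with the event. No document gives a recurrence rate, so the range is shown.

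| Recurrence in each affected person | Events over 21 sessions |
|---|---|
| once only | 27 × 1 = 27 |
| one session in four | 27 × 21 × 0.25 = 141.75 |
| one session in two | 27 × 21 × 0.5 = 283.5 |
| every session | 27 × 21 = 567 |

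The extremes differ by 567 / 27 = 21-fold, and the incidence is 54% in every row.

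**The same question in reverse**

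Take a reported total of 105 events. The fewest people who could produce it is 105 / 21 = 5, which is 5/50 = 10%. It could equally come from all 50, at 105 / 50 = 2.1 events each, which is 100%. The total alone does not distinguish these.

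**Exposure, with the same 27 people and recurrence at every session**

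- 21 sessions: 27 × 21 = 567
- 15 sessions: 27 × 15 = 405
- 10 sessions: 27 × 10 = 270

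If 45 people have 21 sessions and 5 stop at 10 (an assumption), total exposure is 45 × 21 + 5 × 10 = 995 sessions. If the 45 have only 15 each, it is 45 × 15 + 5 × 10 = 725.

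**Early stopping and LOCF**

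Suppose one participant has redness at session 10 only and then stops. Observed data give 1 event. If section 9.8 is applied literally to the 11 sessions not delivered (21 − 10), the last value is carried forward and the total becomes 1 + 11 = 12. If session 10 had been clear, nothing would be added. Early stopping can therefore lower or raise the count, depending on whether LOCF is applied and on the last value recorded.

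**What a participant-level result would give**

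Exact (Clopper-Pearson) 95% limits for k affected of n: the lower limit is the 2.5% quantile of Beta(k, n − k + 1) and the upper limit is the 97.5% quantile of Beta(k + 1, n − k). With n = 50, if all 50 are treated:

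- 27/50 = 54% (39.3% to 68.2%)
- 5/50 = 10% (3.3% to 21.8%)
- 2/50 = 4% (0.5% to 13.7%)

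These can be set beside the percentages in section 1.1. A total of events cannot.

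**The case against.** The strongest reply is that section 9.3.3 mentions neither sessions nor the questionnaire, and nowhere says that a repeat counts as new. A sensible analyst might count redness once per person. The data are held by participant and session, serious events are line-listed (section 8.3), manic symptoms have their own threshold (section 2.6), and percentages could be produced later. This is also a secondary outcome in a single-arm pilot with no safety test.

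Much of this stands, and it rules out several stronger readings that a reader might infer:

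- **That the total will be inflated 21-fold.** That is a bound. It needs redness at every session in every affected person and every repeat counted. The documents support neither as a prediction.
- **That the count measures recurrence and exposure instead of people harmed.** It reflects all three; the difficulty is that they cannot be separated.
- **That early stoppers make tolerability look better.** Section 9.8 leaves the direction open. Poor tolerability would also show in retention and in the recorded reasons for withdrawal (section 6.10).
- **That serious harm would be hidden.** Counts are split by severity, so recurring mild redness swells the mild total and leaves the severe one alone.
- **That the trial cannot inform rates for the next one.** The information will exist. What is missing is a prespecified summary of it.

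The reply does not supply a denominator or a counting rule. No section does, and leaving the choice until the data are in hand is what a SAP is meant to avoid.

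**Conclusion.** The point holds in this limited form. As written, the safety analysis is a count with an undefined unit and no participant denominator, and the proportion of participants with an adverse event cannot be derived from it. The size is best stated as a range of what one incidence or one total could mean: 27 to 567 events for 27 of 50 affected, or 10% to 100% of participants affected for a total of 105 events. Both ranges assume at most one such event per session and full 21-session exposure. The first also reads the 54% in section 1.1 as a share of participants. Neither covers the 3 months of follow-up, which would add further events.

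The actual inflation is unknown because the plan gives no repeat rule and no recurrence rate, and the direction of any bias from early stopping is not determined. The primary outcome is unaffected. The change should be made because safety is a stated objective and a better summary is available from the same data.

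**What to change.** In section 9.3.3:

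1. Make the main safety result the number and percentage of bipolar participants who received at least one tDCS session and had at least one adverse event. Tabulate it by worst severity and by relatedness, with exact 95% confidence intervals. Naming the denominator matters because section 9.7 refers to all participants, and section 6.1 also enrols 35 healthy controls for baseline activities only.
2. Alongside it, for events elicited by the questionnaire, report sessions with the event divided by sessions actually delivered. State that LOCF under section 9.8 does not apply to adverse events, so that none is created for a session that did not take place.
3. Keep the event count as a supplement, with a sentence saying when a recurrence is a new event.
4. State whether each summary covers the treatment period only or also the 3 months in section 8.9.

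The cost is SAP wording and one extra table. No new data collection, visit or sample size change is needed.
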